5 SUBJECTS

5.1 Subject Disposition

The number of subjects that entered the study, withdrawn subjects, completed subjects and the number of subjects at each visit will be summarized by treatment.

5.2 Baseline Characteristics and Demographics

The following baseline characteristics will be given by treatment:

- Age
- Ethnicity
- Weight, height and BMI
- Medical/Surgical history
- UTI history

6 TREATMENT INFORMATION AND EXTENT OF EXPOSURE

6.1 Active Treatment

The number of subjects on each IP will be tabulated with start time, stop time and duration of application will be tabulated using listings and summary statistics.

6.2 Prior and Concomitant Medications

Prior and concomitant medication data will be listed and tabulated by ATC code. Prior and concomitant medications will be coded according to the World Health Organization (WHO) Anatomic Therapeutic Chemical (ATC) classification system.

7 STATISTICAL METHODOLOGY

All parameters will be presented by treatment and visit using summary statistics. Additional statistical analyses are specified below.

7.1 Primary endpoint(s) Analysis

The primary endpoint will be the mean number of confirmed UTIs during six months from start of intervention, as compared to placebo.

The mean number of UTIs per intervention group will be estimated based on the total number of UTIs by subject.

An additional analysis will be made to include the subjects who have been used prohibited medications, long term antibiotics and Hiprex during the study.

7.1.1 Main analytical approach

The mean number of UTIs will be analysed using analysis of covariance with intervention, UTI history and age as independent variables. Sexual activity will only be used in the analysis if it is possible.

7.1.2 Sensitivity analysis

No sensitivity analysis for primary endpoint(s) will be performed.

7.1.3 Supplementary analyses

No supplementary analysis for primary endpoint(s) will be performed.

7.1.4 Presentation

All graphs and tables will be presented in demographic data, section 13.

7.2 Secondary Endpoint(s) Analysis

7.2.1 Definition of endpoint(s)

7.2.1.1 Number of confirmed UTIs

The number of confirmed UTIs for both the:

- Mean number of confirmed UTIs during the three months' intervention period, as compared to placebo.

and

- Mean number of confirmed UTIs during the three months' follow-up period, as compared to placebo.

will be analysed using the same methods as for the primary endpoint.

7.2.1.2 Time to first relapse of UTI

Time to first relapse of UTI will be defined as the time from delivery of intervention (*i.e.* start of intervention) to date of first confirmed UTI ((Confirm date – Intervention date) + 1).

Subjects with no UTI will be censored at last known date within the study period.

The time to first relapse will be analysed using Cox regression analysis and presented by Kaplan-Meier graphs.

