## **10.8 Randomization**

Subjects will be randomized to treatment with active test product or placebo (1:1). A computer-generated randomization list will be created by CTC AB. The randomization will be performed using block randomization within each IP distribution site (these sites will be identified by the Sponsor prior to creating the randomization list). Each distribution site will receive pre-packed boxes with either the test product or placebo, each box marked with a randomization number dedicated to the subject at randomization. The clinic will have a sub-part of the randomization list which contains information about randomization number and distribution site.

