### 16.1 General

Data on continuous variables will be presented using summary statistics. Data will be presented in terms of number (N), arithmetic mean, standard deviation (SD), minimum and maximum value.

Categorical data will be presented as counts and percentages. Individual subject data will be listed by randomization number, and where applicable by assessment time.

All statistical tests will be performed using a two-sided hypothesis with a significance level of 5%.

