3.4 Number of Subjects

The number of subjects needed to verify that the mean number of UTIs during six months for the probiotic will be 0.75 and for placebo 1.35 with a common standard deviation of 1.15, will be 118 (1:1 randomization) using a significance level of 5% and a power of 80%.

Assuming a drop-out rate of 15% a total of 140 subjects will be included, 70 in each intervention arm.

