4.8 Adjustment for Covariates

History of UTIs and age will be used as covariates in the analysis of mean number of UTIs. Sexual activity will only be used as a covariate in the analysis if it is possible.

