7.2.1.3 Relapse rate

The relapse rate for both:

- Proportion of subjects (%) who experienced at least one confirmed UTI during three months from start of intervention, as compared to placebo.

and

- Proportion of subjects (%) who experienced at least one confirmed UTI during six months from start of intervention, as compared to placebo.
will be analysed using Chi-square test without continuity correction and presented using frequency tables.

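### Time to first relapse and the relapse proportions lack the UTI history and age adjustment used for the UTI counts, which costs a little power if those covariates are prognostic

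*SAP*

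**What the plan says.** - **Counts.** SAP 7.1.1 and 7.2.3 analyse the number of UTIs by ANCOVA with intervention, UTI history and age, adding sexual activity if possible. SAP 4.8 sets the scope: "History of UTIs and age will be used as covariates in the analysis of mean number of UTIs". Protocol 16.8.1 limits covariates to the same analysis.
- **Time to first relapse.** SAP 7.2.1.2: "The time to first relapse will be analysed using Cox regression analysis and presented by Kaplan-Meier graphs". SAP 7.2.3 repeats this directly after listing the ANCOVA terms and again names none for the Cox model.
- **Relapse proportions at three and six months.** SAP 7.2.1.3: these "will be analysed using Chi-square test without continuity correction and presented using frequency tables". Protocol 16.6.3 has the same test.
- **Anything else.** SAP 7.2.4 and 7.2.5 rule out sensitivity and supplementary analyses of the secondary endpoints. The table in SAP 3.1 has a supplementary logistic-regression row, but it lists no covariates, and SAP 7.1.3 and 7.2.5 say that no supplementary analysis will be done.
- **Availability.** Age and the UTI history of the previous 12 months are both collected at screening (Protocol 12.3.2, 12.3.5 and Table 9.1).

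**The concern.** All five secondary efficacy endpoints are built from the same UTI events in the same women. Two of them (the period counts) are adjusted for UTI history and age, two (the relapse proportions) are not, and for the fifth (time to first relapse) the model is left open. The plan gives no reason for the difference.

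Three things are at stake. First, in Cox and logistic models, leaving out a baseline predictor of outcome lowers power and moves the estimated hazard or odds ratio towards 1 when there is a treatment effect. Second, a chance imbalance in UTI history would be corrected in the count analyses but not in the relapse analyses, so the two could differ for that reason alone. Third, a Cox model with unstated terms leaves a choice to be made after the data are seen. Protocol 7.3 presents time to relapse as a novelty of this trial, so its model deserves to be fixed in advance.

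**Working it through.** **Inputs.** SAP 3.4 assumes that "the mean number of UTIs during six months for the probiotic will be 0.75 and for placebo 1.35", with SD 1.15, 118 evaluable women, 15% dropout, 5% significance and 80% power. Protocol 16.1 makes the tests two-sided. No power, event count or hazard ratio is stated for the relapse endpoints.

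**1. The plan's own figure.** Normal approximation: n per arm = 2 × (1.960 + 0.842)² × 1.15² / 0.60² = 57.7, so 58 per arm or 116. The t-test version gives 58.64, so 59 per arm or 118, as stated (power 80.2%). Dropout: 118 / 0.85 = 138.8, so 139; the plan says 140.

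**2. Starting power for the relapse endpoints** (assumption: constant rates, 59 per arm).
- Proportions at six months: 1 − exp(−1.35) = 74.1% and 1 − exp(−0.75) = 52.8%. Chi-square power is 68%.
- Proportions at three months: 1 − exp(−0.675) = 49.1% and 1 − exp(−0.375) = 31.3%. Chi-square power is 51%.
- Cox: hazard ratio 0.75 / 1.35 = 0.556 and events 59 × (0.741 + 0.528) = about 75. The Schoenfeld formula gives √(75/4) × |ln 0.556| − 1.96 = about 0.58, so power is 72%.

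**3. How much variation the covariates could explain.** Treat the counts as Poisson given each woman's own rate. The variance is then the mean plus CV² × (mean squared), where CV is the coefficient of variation of the rates. Pooling the arms:
- variance 1.15² = 1.3225
- average mean (0.75 + 1.35) / 2 = 1.05
- average squared mean (0.5625 + 1.8225) / 2 = 1.1925
- CV² = (1.3225 − 1.05) / 1.1925 = 0.2285
- log-rate SD = √ln(1.2285) = 0.45

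UTI history and age cannot explain more than this. A prognostic score with log-hazard SD 0.25 would explain 0.25² / 0.45² = about 30% of it.

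**4. Effect of leaving the score out.** Simulation with 4,000 runs per row, 59 per arm, conditional hazard ratio 0.556, and one normal prognostic score with log-hazard SD s. Hazard ratios are geometric means. Each cell gives unadjusted / adjusted.

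| s | Cox power | Cox HR | 6-month relapse power | 3-month relapse power |
|---|---|---|---|---|
| 0 | 71.4 / 71.6% | 0.550 / 0.547 | 68.1 / 68.2% | 51.6 / 51.5% |
| 0.25 | 68.7 / 70.2% | 0.559 / 0.549 | 64.7 / 66.9% | 49.5 / 50.4% |
| 0.45 | 62.2 / 68.4% | 0.578 / 0.551 | 58.2 / 61.9% | 45.0 / 47.7% |

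Monte Carlo error is about 0.8 points per power figure. With a true hazard ratio of 1, every analysis rejected in about 5% of runs.

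The s = 0.25 row leaves out the other 70% of the variation, so its power levels are on the high side. With that variation kept in, unadjusted Cox power would be about 62% however the variation splits. Adjusted power should then fall between 62% and 68%, so the 6-point ceiling still applies.

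**The case against.** **The unadjusted analyses are legitimate.** A pre-specified chi-square test is a valid choice. An unadjusted hazard ratio is a valid marginal estimate, and type I error is not at risk. These are secondary endpoints with no power target. All of this stands. A reader might infer that the planned tests are biased or invalid, and nothing in the documents supports that.

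**The Cox model is not stated to be unadjusted.** SAP 7.2.1.2 and 7.2.3 list no terms, so covariates are neither included nor expressly excluded. SAP 4.8 makes the unadjusted reading the natural one, but what is certain is an unspecified model. Only the two proportions are definitely unadjusted. This stands, and either reading calls for the same sentence in the SAP.

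**Prognostic strength is unknown.** Every woman has recurrent UTI and is 18 to 50 years old, and postmenopausal women are excluded, which narrows both covariates. A reader might infer a double-digit power loss: at s = 0.7 the same simulation gives 53% against 66% for Cox. But s = 0.7 implies a count SD of √(1.05 + (exp(0.49) − 1) × 1.1925) = 1.34, well above the planned 1.15. The plan's figures do not support a loss of that size.

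**Distribution site.** Protocol 10.8 says "The randomization will be performed using block randomization within each IP distribution site", and a reader might infer that both models also need site terms. Protocol 16.8.3 and SAP 4.9 rule out centre adjustment, the number of distribution sites is not given, and the effect was not quantified. That is a separate question.

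**Conclusion.** The point holds as a modest, low-cost improvement. UTI history and age are confined to the count analyses. The Cox terms are unstated, the relapse proportions are tested without adjustment, and no other planned analysis makes up for it.

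The loss in Cox power runs from none, if the covariates are not prognostic, through about 1 to 2 points at roughly 30% of the between-woman variation, to about 6 points if they explain all of it. In the last case the hazard ratio moves from 0.55 to 0.58, that is, towards 1. Over the same two prognostic cases the loss is about 2 to 4 points for six-month relapse and 1 to 3 points for three-month relapse. These losses come on top of power that, under constant rates, already starts near 72%, 68% and 51%.

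The figures assume constant hazards, exact event times, a single normal prognostic score and 118 evaluable women. The 0.45 bound is approximate, because one common SD does not fit a Poisson mixture in each arm: in the placebo arm the planned variance of 1.3225 is below the Poisson value of 1.35.

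**What to change.** Before unblinding:

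1. **SAP 7.2.1.2:** fit the Cox model with intervention, screening UTI history and age. Define UTI history as the number of UTIs in the previous 12 months and code it as in the ANCOVA; the SAP does not yet define this term for either model.
2. **SAP 7.2.1.3:** analyse relapse at three and six months by logistic regression on the same covariates, and report a standardised risk difference with 95% CI. Keep the frequency table and the chi-square p-value beside it, and say which result is the main one.
3. **SAP 4.8:** extend the covariate statement to these endpoints, and list the change in SAP 8.

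If unadjusted analyses are intended, say so for both endpoints and give the reason.

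The cost is a few sentences and a few lines of code, with no new data. The one drawback is that the hazard and odds ratios become conditional on the covariates, so the Kaplan-Meier curves and raw percentages should stay alongside.

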7.2.1.3 Relapse rate

The relapse rate for both:

- Proportion of subjects (%) who experienced at least one confirmed UTI during three months from start of intervention, as compared to placebo.

and

- Proportion of subjects (%) who experienced at least one confirmed UTI during six months from start of intervention, as compared to placebo.
will be analysed using Chi-square test without continuity correction and presented using frequency tables.

7.2.2 Analysis safety endpoint(s)

7.2.2.1 Adverse events

Adverse events and SAEs will be recorded from start of IP intervention. Medical events occurring between screening and start of IP intervention will be reported separately.

7.2.3 Main analytical approach

The mean number of UTIs will be analysed using analysis of covariance with intervention, UTI history and age as independent variables. Sexual activity will only be used in the analysis if it is possible. No intervention by centre interaction will be possible to apply in this analysis. The estimated intervention difference will be presented by LSMeans and a 95% confidence interval. The time to first relapse of UTI will be analysed using Cox regression analysis and presented by Kaplan-Meier graphs.

7.2.4 Sensitivity analysis

No sensitivity analysis for secondary endpoint(s) will be performed.

7.2.5 Supplementary analyses

No supplementary analysis for secondary endpoint(s) will be performed.

7.2.6 Presentation

The p-values will be included in the summary tables.

7.3 Tertiary/Exploratory Endpoint(s) Analysis

No tertiary/exploratory analysis will be performed.

7.4 Discontinuation

Patients who discontinue from IMP treatment will be tabulated. The reason for discontinuation will be given. For discontinuation due to AE, the AEs will be given.

7.5 Other Analyses

No other analysis will be performed.

7.6 Interim Analysis

No interim analysis will be performed.

8 CHANGES FROM THE CSP

The following have been adjusted regarding to the CSP:

- Sexual activity will only be used in the analysis if it is possible.
- The definition of confirmed and unique UTI's have been added.
- Specify the definition of compliance for PPS.
- Subjects who have been used prohibited medications, long term antibiotics or Hipex during the study will be excluded from PPS.
- Subjects not participated at visit 4 and 7 (3 month and 6 month) will not be included in the PPS population.

9 STATISTICAL DELIVERABLES

The following documents will be delivered:

- SAP
- Statistical analyses and summary tables

10 SOFTWARE

All statistical analyses will be performed using SAS Version 9.4 (SAS institute, Cary, NC).

12 SUPPORTIVE DOCUMENTATION

12.1 Appendix 1. – List of Abbreviations

Abbreviation of term	Explanation
AE	Adverse Event
ATC	Anatomical-Therapeutic-Chemical
BMI	Body Mass Index
CF	Clean File
cfu	Colony-forming units
CRF	Case Report Form
CSP	Clinical study protocol
CTA	Clinical Trial Agreement
CV	Curriculum Vitae
DMP	Data Management Plan
DSM	Deutsche Sammlung von Mikroorganismen
DVP	Data Validation Plan
eCRF	Electronic Case Report Form
EEA	European Economic Area
FAS	Full Analysis Set
GI	Gastro-intestinal
ICF	Informed Consent Form
IEC	Independent Ethics Committee
IP	Investigational Product
N	Number
MedDRA	Medical Dictionary for Regulatory Affairs
PAC	Proanthocyanidin
PPS	Per Protocol Set
RCT	Randomized Clinical Trials
SAE	Serious Adverse Event
SAP	Statistical Analysis Plan
SAR	Serious Adverse Reaction
SAS	Statistical Analysis System
SD	Standard Deviation
SDV	Source Data Verification
SOP	Standard Operating Procedures
SUSAR	Suspected Unexpected Serious Adverse Reaction
TMF	Trial Master File
UTI	Urinary Tract Infection
Enrolled subject	Subject who has signed the Informed Consent Form (ICF)
Screening failure	Enrolled subject not included
Included subject	Subject randomized
Withdrawn subject	Subject randomized but not completed
Completed subject	Subject completed both the intervention and the follow-up periods

12.2 Appendix 2. – Changes to Protocol-Planned Analyses

13 Demographic data

13.1 Demographic information

TABLE 14.1.1.1 SUMMARY OF DEMOGRAPHIC DATA AND OTHER BASELINE CHARACTERISTICS (FULL ANALYSIS SET)

		Treatment A (N=xx)	Treatment B (N=xx)	Total (N=xx)
Age (years)	n/nnmiss	xx/x	xx/x	xx/x
	Mean (SD)	xx.x (x.x)	xx.x (x.x)	xx.x (x.x)
	Median (Min, Max)	xx.x (x, xx)	xx.x (x, xx)	xx.x (x, xx)
Weight (kg)	n/nnmiss	xx/x	xx/x	xx/x
	Mean (SD)	xx.x (x.x)	xx.x (x.x)	xx.x (x.x)
	Median (Min, Max)	xx.x (x, xx)	xx.x (x, xx)	xx.x (x, xx)
Height (cm)	n/nnmiss	xx/x	xx/x	xx/x
	Mean (SD)	xx.x (x.x)	xx.x (x.x)	xx.x (x.x)
	Median (Min, Max)	xx.x (x, xx)	xx.x (x, xx)	xx.x (x, xx)
BMI (M2)	n/nnmiss	xx/x	xx/x	xx/x
	Mean (SD)	xx.x (x.x)	xx.x (x.x)	xx.x (x.x)
	Median (Min, Max)	xx.x (x, xx)	xx.x (x, xx)	xx.x (x, xx)

13.2 Medical/Surgical history

TABLE 14.1.4 MEDICAL HISTORY EVENTS BY SYSTEM ORGAN CLASS AND PREFERRED TERM (FULL ANALYSIS SET)

System organ class Preferred term	Treatment A N=xx			Treatment B N=xx			Total N=xx		
	n(%)	m	n(%)	m	n(%)	m	n(%)	m	n(%)
Total	x(00%)	x	x(00%)	x	x(00%)	x	x(00%)	x	x(00%)
Psychiatric disorders									
Anxiety	x(00%)	x	x(00%)	x	x(00%)	x	x(00%)	x	x(00%)
Depression	x(00%)	x	x(00%)	x	x(00%)	x	x(00%)	x	x(00%)
Insomnia	x(00%)	x	x(00%)	x	x(00%)	x	x(00%)	x	x(00%)
Immune system disorders									
Hypersensitivity	x(00%)	x	x(00%)	x	x(00%)	x	x(00%)	x	x(00%)
Seasonal allergy	x(00%)	x	x(00%)	x	x(00%)	x	x(00%)	x	x(00%)
Metabolism and nutrition disorders									
Type 1 diabetes mellitus	x(00%)	x	x(00%)	x	x(00%)	x	x(00%)	x	x(00%)
General disorders and administration site conditions									
Chronic fatigue syndrome	x(00%)	x	x(00%)	x	x(00%)	x	x(00%)	x	x(00%)
Nervous system disorders									
Narcolepsy	x(00%)	x	x(00%)	x	x(00%)	x	x(00%)	x	x(00%)
Reproductive system and breast disorders									
Premenstrual syndrome	x(00%)	x	x(00%)	x	x(00%)	x	x(00%)	x	x(00%)
Respiratory, thoracic and mediastinal disorders									
Asthma	x(00%)	x	x(00%)	x	x(00%)	x	x(00%)	x	x(00%)
Vascular disorders									
Hypertension	x(00%)	x	x(00%)	x	x(00%)	x	x(00%)	x	x(00%)

n, number of subjects; m, number of events. Percentages are based on the number of subjects in the full analysis set

13.3 Subject disposition and exposure

TABLE 14.1.1.2 SUBJECT DISPOSITION

	Treatment A	Treatment B	Total
Screened subjects	xx	xx	xx
Subjects that entered the study	xx	xx	xx
Withdrawn subjects	xx	xx	xx
Completed subjects	xx	xx	xx
Included in FAS	xx	xx	xx
Included in PPS*	xx	xx	xx
Subjects at Screening	xx	xx	xx
Subjects at Visit 2	xx	xx	xx
Subjects at Visit 3	xx	xx	xx
Subjects at Visit 4	xx	xx	xx
Subjects at Visit 5	xx	xx	xx

13.4 CONCOMITANT MEDICATIONS

LISTING 16.2.5.2.1. CONCOMITANT MEDICATIONS, INDICATIONS (FULL ANALYSIS SET)

Subject Identifier for the Study	Gender	Sequence Number	Reported Name of Drug, Med, or Therapy	Standardized Medication Name	Medication Class Code	Category for Medication	Description	Dose	Dose Units	Route of Administration	Dosing Frequency per Interval
Female xxx	Female	x xxx	xxx	xxx	xxx	Medical/ surgical history	xx	mg	Oral	Daily	
Female xxx	Female	x xxx	xxx	xxx	xxx	Medical/ surgical history	xx	mg	Oral	Daily	
Female xxx	Female	x xxx	xxx	xxx	xxx	Medical/ surgical history	xx	mg	Oral	As needed	

13.5 Primary Endpoint: XXXX

TABLE 14.2xx XXXXX (μg/l)

Variable	Result Category	Visit Name	Treatment A		Treatment B	
			Measured value	Visit 1 Baseline	N	Mean (SD)
			Median (Min, Max)		xx (xx, xx)	xx (xx, xx)
			95% CI		xx;xx	xx;xx
Visit 2	N				xx	xx
			Mean (SD)		xx (xxx)	xx (xxx)
			Median (Min, Max)		xx (xx, xx)	xx (xx, xx)
			95% CI		xx;xx	xx;xx
Absolute change from baseline	Visit 2	N			xx	xx
			Mean (SD)		xx (xxx)	xx (xxx)
			Median (Min, Max)		xx (xx, xx)	xx (xx, xx)
			95% CI		xx;xx	xx;xx
			Between groups p-value (Wilcoxon)		0.0000	0.0000
			Within group p-value (Wilcoxon)		0.0000	0.0000
Percent change from baseline (%)	Visit 2	N			xx	xx
			Mean (SD)		xx (xxx)	xx (xxx)
			Median (Min, Max)		xx (xx, xx)	xx (xx, xx)
			95% CI		xx;xx	xx;xx
			Between groups p-value (Wilcoxon)		0.0000	0.0000
			Within group p-value (Wilcoxon)		0.0000	0.0000

13.6 Continuous variables measured over time

TABLE 14.2.xx Variables over time

Variable	Result Category	Visit Name	Treatment A		Treatment B	
			xx	xx	xx	xx
xxxxx	Measured value	Visit 1 Baseline	N	Mean (SD)	xx (xxx)	xx (xxx)
				Median (Min, Max)	xx (xx, xx)	xx (xx, xx)
	95% CI				xx;xx	xx;xx
xx	N		xx	Mean (SD)	xx (xxx)	xx (xxx)
				Median (Min, Max)	xx (xx, xx)	xx (xx, xx)
	95% CI		xx;xx		xx (xx, xx)	xx (xx, xx)
Absolute change from baseline	xx	N	xx	Mean (SD)	xx (xxx)	xx (xxx)
				Median (Min, Max)	xx (xx, xx)	xx (xx, xx)
	95% CI		xx;xx		xx (xx, xx)	xx (xx, xx)
	Between groups p-value (Wilcoxon)		0.0000		0.0000	0.0000
	Within group p-value (Wilcoxon)		0.0000		0.0000	0.0000
Percent change from baseline (%)	xx	N	xx	Mean (SD)	xx (xxx)	xx (xxx)
				Median (Min, Max)	xx (xx, xx)	xx (xx, xx)
	95% CI		xx;xx		xx (xx, xx)	xx (xx, xx)
	Between groups p-value (Wilcoxon)		0.0000		0.0000	0.0000
	Within group p-value (Wilcoxon)		0.0000		0.0000	0.0000

13.7 Continuous variables measured at one occasion

TABLE 14.2.xx Variables at one occasion

Variable	Result Category	Visit Name	Treatment A		Treatment B	
			N	Mean (SD)	N	xx
xxxxx	Measured value	xxx	xx	xx (xxx)	xx	xx
				xx (xx, xx)	xx (xx, xx)	xx (xx, xx)
				xx;xx	xx;xx	xx;xx
				95% CI	95% CI	95% CI
				Between groups p-value (Wilcoxon)	0.xxxx	0.xxxx

13.8 Categorical variables at different visits

TABLE 14.2.xx categorical variables over time

		Treatment A (N=xx)	Treatment B (N=xx)	Total (N=xx)
Prevalence of XXXXXX visit x	No	xx (xx%)	xx (xx%)	xx (xx%)
	Yes	xx (xx%)	xx (xx%)	xx (xx%)
Chi-Square p-value				0.xxxx
Prevalence of XXXXXX visit x	No	xx (xx%)	xx (xx%)	xx (xx%)
	Yes	xx (xx%)	xx (xx%)	xx (xx%)
Chi-Square p-value				0.xxxx
Prevalence of XXXXXX visit x	No	xx (xx%)	xx (xx%)	xx (xx%)
	Yes	xx (xx%)	xx (xx%)	xx (xx%)
Chi-Square p-value				0.xxxx
Prevalence of XXXXXX visit x	No	xx (xx%)	xx (xx%)	xx (xx%)
	Yes	xx (xx%)	xx (xx%)	xx (xx%)
Chi-Square p-value				0.xxxx
Prevalence of XXXXXX visit x	No	xx (xx%)	xx (xx%)	xx (xx%)
	Yes	xx (xx%)	xx (xx%)	xx (xx%)
Chi-Square p-value				0.xxxx

